11. STATISTICS AND ANALYSIS

11.1. Statistical Analysis Plan (SAP)

The plan for the statistical analysis of the trial are outlined below. There is no separate SAP document in use for the trial.

11.2. Description of the Statistical Methods

Outcome Measures

We will adopt clear criteria for progression to a large-scale clinical study. If all criteria are met (green) we will proceed to apply for future funding for a full clinical study with the same protocol; if one or more

criteria is amber, we will adapt the protocol to address the shortfall and re-assess, and any red criteria will prompt major changes to study design or non-progression.

The major feasibility outcomes are as below (includes all sites) and are to be applied once all centres are actively recruiting:

	Green	Amber	Red
1. Average monthly recruitment	≥1.5	0.5-1.5	<0.5
(pts / month)*			
2. Proportion of data completion	³ 90%	75%-90%	<75%
(VAS, QOL) in those capable of			
completing (i.e. not including			
those who have died during trial			
follow up)			
3. Data availability - time to	≥90%	75%-90%	<75%
diagnosis			
4. Proportion completing study	≥90%	80-90%	<80%
protocol in those who are still			
alive at end of follow up			
5. Proportion of eligible patients	>50%	30-50%	<30%
randomised			

*Once all centres have been greenlighted

In depth screening logs will be maintained at recruiting centres, in order to calculate the proportion of eligible patients and the proportion accepting randomization to the study protocol. A patient is considered to be eligible if they fulfil all of the inclusion criteria and none of the exclusion criteria. Screening logs will be reviewed by the central trial team on a monthly basis once all centres have been greenlighted.

Secondary outcomes:

- Mean change and SD in 100mm visual analogue score for breathlessness. This is the current proposed primary outcome measure for a definitive clinical trial and will be measured over follow up.
- Time to actionable histopathology (MDT consensus, referral for oncological treatment)
- Healthcare utilization number of pleural procedures over 3 months follow up
- Patient anxiety and depression over the diagnostic pathway period (hospital anxiety and depression score (HADS), quality of life by QLQ-C30 tool)
- All-cause mortality (retrospective electronic patient record review)

Data and Statistical Analysis

Feasibility parameters will be analysed for the overall trial and for each individual arm of the trial. The mean / median and variability of each major outcome will be calculated, to power a potential future definitive study.

Initial comparisons between randomised groups will be conducted for the major outcome measures to assess for early signals. Data will be analysed with the assistance of a dedicated statistician ([name]) using a mixed effects regression model to account for repeated sampling over 3 months.

Qualitative Interview Analysis

Structured qualitative interviews will be thematically analysed. The trial fellow [name] with consultancy provided by the specialist qualitative team at Oxford Brookes University will undertake inductive coding to develop a coding framework. code lists before applying them to the entire dataset. Coded elements of the interview transcripts will be combined into categories and themes identified from patterns in the dataset for reporting.

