2. LAY SUMMARY

A malignant pleural effusion (MPE) is a buildup of fluid around the lungs due to any type of cancer that has either started or spread to the lining of the lungs (pleura). This is a very common problem, effecting over 100 people per day in the UK. Typically, people with MPE experience debilitating breathlessness due to fluid buildup. Another challenge for people suffering with MPE is the challenge to reach a diagnosis which can delay treatment with, for example chemotherapy.

At present, in the standard investigation and management pathway for patients with a pleural effusion suspected to be due to cancer, patients have some fluid drawn off and the cells analysed for the presence of cancer cells. This often is not successful and recent data from our site has suggested only 20% of patients receive enough information from fluid alone to treat their cancer. The patient therefore has to come back for a biopsy of the lining of the lung. Once a diagnosis is secured, steps to stop the fluid around the lungs coming back are taken, one of which is to insert a long-term tube in the chest (indwelling pleural catheter, IPC) which is dressed and can be used a few times per week to let fluid out (done by a district nurse or carer at home). Typically, with the current pathway, patients wait 6 weeks for a diagnosis and over 2 months for long term control of breathlessness. Many of these patients have a life expectancy of 3-12 months and as such a large proportion of this is spent breathless and without a diagnosis.

We aim to create a new accelerated pathway (diagnosing and managing fluid build up, which is all part of standard care) for patients suffering with potential MPE, such that at their first visit, patients will be offered a biopsy which give them the highest likelihood (80-95% success rate), of reaching a diagnosis and in the same (first) visit, the patients will have a long term chest tube fitted (indwelling pleural catheter, IPC) so they are not left breathless and needing multiple procedures. This could achieve diagnosis and treatment in one procedure rather than multiple separate procedures in the standard pathway.

Our study will randomise patients in to either a group having the current standard care pathway, or into the accelerated pathway. We will assess key parameters such as the time to diagnosis, overall duration of breathlessness while awaiting a diagnosis, and quality of life.

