9.8. Subsequent Visits

The follow up period is 12 weeks post procedure Trial follow up appointments will take place at

- 2 weeks ± 3 days
- 6 weeks ± 5 days and
- 12 weeks ± 7 days post procedure

This follow up schedule mirrors normal clinical care. Appointments should take place at the patient's local centre.

Data collected at each follow up will be:

1. VAS diary (week 2, 6 visit)

2. QLQ C30, EQ 5D 5L, and HADS diary (week 2, 6 visit)

3. Side effects attributable to the trial intervention

4. Information on healthcare utilisation including inpatient and outpatient admissions for pleural effusion management and any other cause

5. Ultrasound and Chest X Ray will be conducted at 2 weeks and 6 weeks as part of standard care, and results documented on the CRF.

At each follow up visit participants will undergo a standard clinical consultation, which should be conducted by a medical member of the trials team and the appropriate CRF should be completed. A chest x-ray (and ultrasound if available) should be performed (as per routine clinical care) and the results entered into the CRF. Participant completed diaries will be reviewed at these visits.

Participants will be asked to complete a home VAS diary three times per week and Quality of Life scores (1 per week) for 6 weeks post index procedure.

In light of the COVID-19 pandemic it is possible that participants and/or sites will judge that participant contact should be minimised. In recognition of this, follow up visits at 12 weeks may be carried out remotely via telephone.

Reasonable travel expenses to participants for visits that do not align with clinical care will be covered as part of the per participant costs. All feasible efforts have been made to align clinical and study visits, however, 'non-aligned' visits may occur in cases, for example whereby participants have required clinical review outside the study visits and thus are required to attend for a study visit sooner than otherwise required.

Visual Analogue Scale (VAS) scoring

VAS outcomes will be captured using participant paper diaries. Following hospital discharge, participants will receive a trial nurse phone call once per week, according to local availability, as a reminder to complete the VAS scores. The schedule of VAS scores is as follows:

• Pre-procedure VAS (day of first procedure, immediately prior).

- Post procedure VAS (day of the procedure, before discharge)

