11.3. Sample Size Determination

As a feasibility study, sample size has not been formally calculated. However, other feasibility studies looking at interventions in MPE have typically used 30 to 50 participants^{22 23}.

In a potential future definitive study of the accelerated pathway, mean difference in VAS (for which the MCID is 19mm) would be a likely primary outcome measure. In such a study, 170 participants would be sufficient to detect a mean difference of 19mm between the two arms (5% significance, 90% power) assuming an SD of 35mm based on previous MPE studies⁷.

If a quality of life measurement was preferred as the primary outcome, the MCID in global health status based on reference values provided by the EORTC Quality of Life Group is 8 points.190 patients would achieve a 90% power to detect an 8 point difference^{24 25} with a common SD within group of 23.6, derived from EORTC reference values.

Thus, in a future 8-centre study, a recruitment target of 190 patients (powered for VAS or QOL) could be achieved in 18 months if recruitment occurs at approximately 1-2 participants per centre per month. **Therefore, the recruitment target for our proposed feasibility study is 1-2 participants per month.**

We propose 40 patients to allow for 10% attrition and based on likely recruitment rate within the study timetable.

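### Progression criterion 2 leaves out everyone who dies within the 12-week follow-up, although the diaries it scores stop at week 6

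*Protocol*

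**What the plan says.** The progression table in Protocol section 11.2 has five criteria. Criterion 2 is the proportion of data completion, "VAS, QOL) in those capable of" completing them, and the bracket that explains this removes "those who have died during trial" follow-up. Green is 90% or more, amber 75% to 90%, and red below 75%.

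Section 9.8 fixes the length of follow-up: "The follow up period is 12 weeks post procedure". The forms that criterion 2 scores cover a shorter period. Section 9.8 asks for a VAS diary three times a week and "Quality of Life scores (1 per week) for 6 weeks post index procedure". Footnotes 3 and 4 of the schedule table in section 9 give the same six weeks, as does section 9.7 for the home diary. At visits, section 9.8 collects the "QLQ C30, EQ 5D 5L, and HADS diary (week 2, 6 visit").

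Section 11.1 states that no separate SAP is in use, so the table in section 11.2 is the operative definition. Under section 11.8, missing data are reported but not adjusted for.

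**The concern.** The exclusion does not match the purpose stated in the same row. Someone who dies in week 10 was alive on every diary day, so death cannot explain a blank form, yet the whole person leaves the denominator. Someone who dies in week 5 loses about four weeks of forms that fell due during life. Removing forms due after death is legitimate; removing the person is not.

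The result feeds a decision. If all criteria are green, the team applies for funding for a full study with the same protocol. An amber result means adapting the protocol and reassessing. The VAS is also the proposed primary outcome of the definitive trial, so its completeness is one of the main things this study is meant to measure.

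**Working it through.** The protocol gives no expected completeness and no expected number of deaths, so there is no figure of its own to reproduce.

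**Step 1. Windows side by side**

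| Item | Period | Source |
|---|---|---|
| VAS diary | pre- and post-procedure, then 3 per week to week 6 | 9.8; schedule footnote 3 |
| Quality-of-life forms | pre-procedure, then weekly to week 6 | 9.8; schedule footnote 4 |
| Deaths removed by criterion 2 | any time to week 12 | 11.2 with 9.8 |

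The exclusion window is twice the diary window.

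**Step 2. How many participants outlive the diary and are still removed**

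Inputs: N = 40 (section 11.3) and the survival statement "Many of these patients have a life expectancy of 3-12 months" (section 2; section 5 gives the same range). Assumptions: the range is one of medians, and survival is exponential. The share dead by t weeks is 1 − 2^(−t/m), with m the median in weeks (months × 52.18/12).

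| Median | Dead by week 6 | Dead by week 12 | Weeks 6-12 | Of 40 | Share of all removed |
|---|---|---|---|---|---|
| 3 months | 27.3% | 47.1% | 19.8% | 7.9 | 42% |
| 6 months | 14.7% | 27.3% | 12.6% | 5.0 | 46% |
| 12 months | 7.7% | 14.7% | 7.1% | 2.8 | 48% |

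On this reading 3 to 8 participants are removed although they lived through the whole diary period, a little under half of all those removed.

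**Step 3. Effect on the reported percentage**

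Let p be the share dying by week 12. Suppose half of them die by week 6, with half their forms due on average. Survivors complete a share s, and decedents a share d of the forms due while alive.

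- Forms due per participant, with a full diary = 1: (1 − p) + p/2 + p/4 = 1 − p/4
- Forms completed: (1 − p)·s + (3p/4)·d
- Criterion 2 as written reports s

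With p = 0.25 and s = 0.92, forms due are 0.9375 and forms completed are 0.69 + 0.1875·d:

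- d = 0.50: 0.7838/0.9375 = 83.6% (amber)
- d = 0.70: 0.8213/0.9375 = 87.6% (amber)
- d = 0.85: 0.8494/0.9375 = 90.6% (green)
- d = 0.92: 92.0%, no bias

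The colour changes when d falls below (0.90 × 0.9375 − 0.69)/0.1875 = 0.82. The values of s and d are illustrations; the protocol gives neither.

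**Step 4. Sensitivity**

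- Exponential model, 6-month median, s = 92%, d = 70%: 92% as written, 88.8% if only deaths by week 6 are removed, and 87.3% on forms due while alive.
- p = 0.25, s = 97%, d = 70%: (0.7275 + 0.1313)/0.9375 = 91.6%, still green.
- p = 0.15, s = 92%, d = 80%: (0.782 + 0.09)/0.9625 = 90.6%, still green.
- Exponential model, 6-month median, s = 88%, d = 100%: 88% (amber) as written against 90.6% (green). The bias reverses.

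**The case against.** The strongest reply is that the direction of any bias is not fixed. Bias arises only if participants who later die complete a different share of their forms while alive from survivors. The green-to-amber example places survivors just above the 90% cut and decedents well below it, and nothing in the protocol supports either value. Step 4 shows cases where the colour does not change and one where it moves the other way. This stands: a reader might infer that completeness will be overstated, but the documents show only that it can be.

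The count of 3 to 8 is also conditional. The protocol never calls 3 to 12 months a median. If it is a range of individual survival, few or no deaths fall within 12 weeks. The trial also enrols suspected rather than proven malignant effusion, excludes WHO performance status 3 or worse, and expects a few diagnoses other than cancer. This stands as a limit on the size, not on the mismatch.

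Third, the schedule table appears to tick quality of life at week 12, against its own footnote 4 and section 9.8, and section 11.2 speaks of repeated sampling over 3 months. The table may have been damaged in extraction. If a week 12 form is due, a participant who dies in week 10 was not alive for every quality-of-life form. That does not affect the VAS, and it would not justify deleting the forms due before death.

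Finally, section 11.8 promises to report missing data, and all-cause mortality is an outcome. This softens the consequence for planning a later trial, but the progression decision is still tied to the percentage as defined.

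Two further inferences are tempting and are not supported:

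- That "We propose 40 patients to allow for 10% attrition" contradicts the stated survival. Attrition is not defined, it is not said to include deaths, and section 11.3 says the size was not formally calculated.
- That criterion 4 has the same fault. It is restricted to those "alive at end of follow up", but it measures completion of a 12-week protocol, so its condition and its window agree.

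**Conclusion.** The mismatch in criterion 2 is real and can be read directly from sections 11.2 and 9.8: the denominator is conditioned on 12-week survival, while the VAS diary and weekly quality-of-life forms run for six weeks. It removes participants who were able to complete every VAS entry, and it discards forms that earlier decedents owed while alive.

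The size is conditional. About 3 to 8 of 40 participants outlive the diary and are removed, if 3 to 12 months is a range of exponential medians. The reported percentage is too high only if decedents complete fewer of their forms while alive than survivors. That is plausible in a population that declines before death, but the documents do not establish it. With 25% deaths, survivors at 92% and decedents at 50-70%, the gap is 92% against 84-88%, enough to turn amber into green. With similar completion there is little or no bias. The definition should be corrected because it drives a progression decision, whichever way the bias runs.

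**What to change.** Define criterion 2 as VAS and quality-of-life forms completed divided by forms due while the participant was alive, up to week 6. Count forms after dropout as missing, and remove only forms due after the date of death. Report deaths separately, by arm.

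Reconcile the apparent week 12 quality-of-life tick in the schedule table with its footnote 4 and section 9.8, so that the quality-of-life window is settled before the denominator is fixed.

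The cost is one definition and one table correction. Diary entries and mortality are already collected, so no new data are needed. The downside is that completeness may look less favourable against the 90% threshold.

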Pilot work has demonstrated that the total duration of this pathway is long. Patients experience significant breathlessness between repeated procedures, and there is an average of 30 days to diagnosis and 70 days to definitive pleural fluid and breathlessness control. Leveraging the modern data, this suggests that a new and accelerated pathway should be considered for both a quicker diagnosis, and better symptom control from the patient perspective.

The Patient Perspective

Published work in this area has ignored the vital patient perspective in terms of priorities of diagnosis and symptom management. Pleural aspiration does not prevent fluid recurrence and further

breathlessness; approximately 30% of patients will experience fluid recurrence within two weeks following aspiration and this increases over time⁴.

Patients thus often undergo multiple procedures for symptoms, while waiting for final diagnostics and definitive management. Patients experience significant uncertainty and anxiety within this pathway⁵. Pilot PPI data (n=17) demonstrates 84% of patients with MPE had undergone 2 or more procedures prior to indwelling catheter insertion and 65% had been breathless for over one month, with 60% having to make an emergency call for fluid drainage or admission to hospital. The ~70 day pathway length is similar in other pleural centres (Bristol, Glasgow) and likely longer in non-specialist units. This duration forms an unacceptable proportion of the 3-12 month total survival in patients with MPE.

Summary: The current MPE pathway results in prolonged breathlessness and long delays to an 'actionable diagnosis' (i.e. information that can guide systemic cancer treatment).

Benefits to patients and addition to current research

The proposed study seeks to target the delay to diagnosis and prolonged breathlessness by combining a definitive diagnostic procedure (pleural biopsy) and fluid management (IPC) as the **first intervention**. This will achieve an earlier diagnosis, fluid control, and control of breathlessness as early as possible in the diagnostic pathway. The novel pathway has the potential to provide months of additional symptom benefit, reduce time to diagnosis, prevent multiple repeat procedures and reduce costs.

Work from our unit and others has shown the unacceptable diagnostic delays, prolonged breathlessness and repeated procedures in patients with MPE⁶.

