11.4. Analysis populations

The study will be analysed on intention to treat, with included populations as specified above.

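### Progression criterion 2 removes everyone who dies within 12 weeks, along with the VAS and QOL forms due while they were alive, so completion is measured in survivors only and may read too high

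*Protocol*

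**What the plan says.** Section 11.2 lists five progression criteria. The second is headed "2. Proportion of data completion" and restricted to "VAS, QOL) in those capable of" completing. A bracket then explains capability as not including "those who have died during trial" follow-up. The exclusion is of people, not of forms. Green is 90% or more, amber 75% to 90%, red below 75%.

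Section 9.8 sets the two time windows: "The follow up period is 12 weeks post procedure", while participants are asked to complete "a home VAS diary three times per week and Quality of Life scores (1 per week) for 6 weeks post index procedure". Footnotes 3 and 4 of the schedule in section 9 agree with the 6-week limit. The body of the same schedule, however, also marks QOL at week 12.

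Nothing elsewhere brings the excluded forms back into this criterion. Section 11.8 has missing data reported without adjustment, and section 11.1 says that no separate SAP is in use. Criterion 4 is also limited to participants alive at the end of follow-up.

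**The concern.** Death should stop further forms from falling due. It should not cancel forms that were already due. As written, a death in week 8 removes a complete 6-week diary period, and a death in week 5 removes the forms due in the weeks before it. Neither person was incapable of completing those forms, so the rule goes further than its stated purpose.

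The people removed are those closest to death, in whom missed forms are plausibly most frequent. Section 5 cites a "3-12 month total survival in patients with MPE", so some deaths within 12 weeks are to be expected.

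Data completeness is part of the primary outcome (section 6). All-green criteria lead to a funding application with the same protocol, and an amber criterion leads to adapting it. Breathlessness VAS is the proposed primary outcome of the definitive trial. Whether people who later die return their diaries is something this study should find out, and no progression criterion measures it.

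**Working it through.** The protocol states no figure to reproduce here: the 90% and 75% cut-offs are set, not derived, and no completion or mortality rate is given. The check asks how many due forms the rule discards and how far the reported percentage could move.

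**Inputs from the protocol.** 40 participants; 12-week follow-up; forms due are 20 VAS (before and after the procedure, then 3 × 6 = 18 at home) and 7 QOL sets (before the procedure, then 6 weekly), so 27 occasions; survival of 3 to 12 months (section 5); 10% attrition (section 11.3).

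**Assumptions.** Constant hazard; the 3 and 12 months read as medians, with 6 months between; survivors complete 92%; those who die complete a proportion *c* of the forms due while they were alive. As an alternative, the 10% attrition is read as deaths by week 12.

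**Formulas.**
- Survival: S(t) = exp(−ln 2 × t / median). For the alternative, the daily hazard is −ln(0.9)/84 = 0.00125.
- Forms due while alive, per participant: D = sum of S(t) over the 27 occasions.
- Share of due forms discarded: d = 1 − 27 × S(84) / D.
- Completion as written: 92%, whatever *c* is.
- Completion of all forms due while alive: 0.92 − (0.92 − c) × d.
- Value of *c* below which the all-forms figure drops under 90%: 0.92 − 0.02/d.

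**Example, 12-month median.** S(84) = exp(−0.6931 × 84 / 365.25) = 0.853. D = 25.99. d = 1 − 27 × 0.8526 / 25.99 = 0.114. With c = 0.60: 0.92 − 0.32 × 0.1143 = 88.3%.

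| Survival assumption | Deaths of 40, weeks 0–6 | Deaths, weeks 7–12 | Deaths by week 12 | Due forms discarded | c = 60% | c = 75% | c = 92% | c = 95% | Green lost below c of |
|---|---|---|---|---|---|---|---|---|---|
| Median 12 months | 3.1 | 2.8 | 5.9 | 11.4% | 88.3% | 90.1% | 92.0% | 92.3% | 74.5% |
| Median 6 months | 5.9 | 5.0 | 10.9 | 21.6% | 85.1% | 88.3% | 92.0% | 92.6% | 82.7% |
| Median 3 months | 10.9 | 7.9 | 18.9 | 38.7% | 79.6% | 85.4% | 92.0% | 93.2% | 86.8% |
| 10% attrition read as deaths | 2.1 | 1.9 | 4.0 | 7.7% | 89.5% | 90.7% | 92.0% | 92.2% | 66.0% |

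Between 42% and 48% of the deaths under the three medians fall in weeks 7 to 12, after the diary has ended. Using the 18 home VAS entries alone gives almost the same shares: 77 of 691, 139 of 663 and 231 of 611 entries (11%, 21% and 38%) for medians of 12, 6 and 3 months.

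**If the week-12 QOL set counts as due.** It adds S(84) to D and nothing to the discarded forms, because people who die before week 12 never owe it. Over 40 participants, d becomes 118.8/(1039.7 + 34.1) = 11.1%, 216.3/(1001.5 + 29.1) = 21.0% and 360.3/(931.2 + 21.1) = 37.8%. The finding does not depend on which reading is adopted.

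**The case against.** The strongest objection is that the upward direction is assumed. The protocol gives no completion rates. With equal completion the two figures coincide, and if those who die return 95%, the written figure is slightly low. This stands: a reader might infer that the criterion is shown to be biased towards green, and the documents do not show that.

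The size also depends on the inputs. Survivor completion of 92% lies only two points above the cut-off. At 97%, with a 12-month median and 60% before death, the all-forms figure is 0.97 − 0.37 × 0.114 = 92.8%, green either way. Nor are the 3 to 12 months stated to be medians. The trial excludes WHO performance status 3 or worse and expects a few non-cancer diagnoses, so survival may be longer, and 19 deaths of 40 is hard to square with a 10% attrition allowance. If that 10% means deaths, the effect for 60% to 75% completion is 1.3 to 2.5 points. All of this stands as a limit on the size, not on the defect.

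A reader might also see a conflict with section 11.4, "The study will be analysed on intention to treat". There is none: the same sentence goes on to refer to populations specified earlier in the plan, and intention to treat does not fix the denominator of a descriptive feasibility proportion.

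Nor does the rule remove data elsewhere. Missing data and all-cause mortality are reported, and nothing takes diary entries made before death out of the mixed model. The blind spot is confined to this criterion.

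Finally, a lenient reader could take the bracket to drop only forms due after death. That would cure the problem, but the bracket names people.

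**Conclusion.** The point holds as a defect in the denominator of criterion 2. The criterion measures completion in 12-week survivors, against forms that mostly fall due by week 6, and so discards forms that people were alive to complete. That follows from the text and needs no assumption.

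The share discarded does rest on assumptions: about 11% to 39% for constant-hazard medians of 12 to 3 months, and about 8% if the attrition allowance is read as deaths. With survivors at 92%, the written figure is green regardless. Under the three medians, the all-forms figure runs from about 80% to 90% when those who die return 60% to 75%, which is amber except at the most favourable corner (12-month median with 75%: 90.1%, still green). A change of colour is therefore possible but not established, and amber calls for adapting the protocol and re-assessing, not for stopping. The change should be made, because a progression rule ought to be unambiguous before results are seen and the correction is cheap.

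**What to change.** Redefine criterion 2 as VAS and QOL forms completed divided by forms due while the participant was alive, over all randomised participants. Forms cease to fall due at death or at the end of the scheduled form period, whichever comes first. Keep the 90% and 75% cut-offs, and report the survivors-only figure alongside, with the number of deaths.

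Reconcile the week-12 QOL mark in the section 9 schedule with footnote 4 and section 9.8, so that the set of due forms is fixed before completion is calculated.

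The cost is one sentence in section 11.2 and one correction to the schedule or its footnote. The redefinition needs no data beyond form dates and dates of death. The reported completion figure may be less favourable.
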